11.0 Statistical/Data Analysis Plan

11.1 Data Analysis Plan and Statistical Considerations:

List the statistical methods to be used to address the primary and secondary objectives, specific aims, and/or research hypotheses. Explain how missing data and outliers will be handled in the analysis. The analysis plan should be consistent with the study objectives. Include any subgroup analyses (e.g., gender or age group). Specify statistical methods and variables for each analysis. Describe how confounding variables will be controlled in the data analysis.

Demographic (age at time of surgery, BMI, sex, active duty/dependent/retiree status), medical (ICD code, nicotine use, history of diabetes, prior pain medications), laterality of the TKA (left or right), discharge disposition, and anesthetic block type (spinal, adductor, or femoral nerve block) data will be summarized overall and as a function of injection group using descriptive statistics (eg, mean, standard deviation, median, minimum, maximum, frequency, percentages) and 95% confidence intervals to describe the sample. Appropriate inferential statistics (eg, independent samples t tests, chi square tests) will be performed to determine if there are statistically significant differences in any of these variables between the two injection groups. If so, multivariable techniques (eg, ANOVA or regression) including these potentially confounding variables in the analyses and/or stratification will be undertaken.

VAS pain scores and the dosage (MME) of opioids will be evaluated in patients as a function of injection type (ie, trigger point injection vs. sham injection) at each time point. Data will be assessed for normality and homogeneity of variance to determine whether parametric (eg, independent samples t tests, repeated measures ANOVAs) or nonparametric (eg, Wilcoxon Mann Whitney tests, Skillings-Mack tests) methods are appropriate.

In addition, the number of patients with a VAS>40 (indicating a “significant” level of pain) will be calculated and compared in each group and at each time point using the chi-square test (or the Fisher’s Exact test if assumption regarding minimum expected cell counts is not met) as well as McNemar’s tests.

The critical alpha level will be set at .05. Missing data will be handled using the “pairwise deletion” method; this method still includes patients with some missing data in the analyses when possible.

The plan is to use 10-15 participants per group, although if time and resources permit, we will include more patients to increase the power of the study and

account for possible dropouts up to a maximum of 50 patients per group. Recruitment and enrollment will end once the target sample size has been achieved.

11.2 Sample Size:

The plan is to use 10-15 participants per group, although if time and resources permit, we will include more patients to increase the power of the study and account for possible dropouts up to a maximum of 50 patients per group (maximum of 100 patients total).

11.3 Total number of subjects requested (including records and specimens):

100

11.4 If you are recruiting by study arm, please identify the arms of the study and how many subjects will be enrolled in each arm

Experimental (ie, trigger point injection) group will include 10-15 patients (up to a maximum of 50 patients) and placebo (ie, sham injection) group will include 10-15 patients (up to a maximum of 50 patients). Recruitment and enrollment will end on 31 December 2025.

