The aim is of this study is to explore the effect of a pain intervention (ie, trigger point injection) vs. a sham injection on managing post-surgical pain and reducing the reliance on systemic opioid analgesics. Outcomes include the VAS on POD1 and week 2 and week 6 follow-up appointments. Opioid use will also be evaluated during these intervals.

9.4 Study Design:

Describe study design in one to two sentences (e.g., prospective, use of existing records/data /specimens, observational, cross-sectional, interventional, randomized, placebo-controlled, cohort, etc.). Specify the phase – Phase I, II, III, or IV – for FDA-regulated investigational drug research

Prospective, interventional study comparing trigger point injections vs. sham injections on VAS pain scale ratings and opioid use.

9.5 Target Population:

Describe the population to whom the study findings will be generalized

DoD beneficiaries aged 45 years and older who will be receiving a TKA, on either knee.

9.6 Benefit to the DoD:

State how this study will impact or be of benefit to the Department of Defense

The purpose of this study is to explore a unique pain management modality to reduce the use of opioids following a routine surgery in the military hospital setting. This will benefit the Department of Defense by improving post surgical pain, decreasing overall opioid use which in turn may lead to decrease rate of opioid use disorders, shorter inpatient stays and decrease adverse medication side effects.

10.0

Study Procedures, Data Management, and Privacy

10.1 Study Procedures:

Describe step-by-step how the study will be conducted from beginning to end

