those in the sham injection group an S. The study participants will not know which study group they will be assigned to. An equal number of participants will be included in each group (ie, trigger point injection vs. sham injection).

Step 3a: (Trigger point injection group) The principal investigator will identify relevant structures to include the vastus medialis, vastus lateralis, medial, and lateral gastrocnemius muscle bellies by utilizing anatomical landmarks. Once those structures are identified, each area will be prepped in an aseptic fashion with alcohol swabs. Two injections will be made in each muscle belly. Each injection will include 0.5 mL of 1% lidocaine without epinephrine. A total of eight injections will be administered with a total of 4 mLs of 1% lidocaine without epinephrine using a 1 ½" 25-gauge needle. A separate needle and syringe will be utilized for each of the four muscle bellies. Careful consideration to avoid neurovascular structures will be taken by retracting the plunger to ensure needle placement is outside vascular structures with each injection. A blind will be placed between the patient and the needle in order for the patient not to witness the injection, which is the same protocol as the sham injection. The blind used will be a drape or other soft item held by a person not involved with the study to obscure the vision of the subject during the injection and allow the investigator to use both hands to safely conduct the injection and aspiration procedure. The local anesthetic will be massaged into the area to ensure the medication disperses thoroughly into the muscle belly. After the needle is removed, the area will be cleaned with alcohol swabs and a bandage will be applied. This will be completed on POD 0 (ie, the day of the TKA procedure). Within the informed consent the consenting verbiage will ensure that the participants will not be able to identify injection technique that will identify whether they are in the sham or experimental group.

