Step 3b: (Sham injection group) The principal investigator will identify relevant structures to include the vastus medialis, vastus lateralis, medial and lateral gastrocnemius muscle. Once those structures are identified using anatomical landmarks, each area will be prepped in an aseptic fashion with alcohol swabs. A needle with a syringe filled with sterile water will be inserted into the epidermis to mimic an actual trigger point injection. The needle will be left in place for 3-5 seconds to create the false perception of injection anesthetic into the muscle groups. No sterile water will be injected into the participant. Since the effects from the anesthetic block will still be active and the injections will be administered in a position that prevents the participant from viewing the procedure, participants will not know that there is nothing being injected into the area. This will occur by placing a blind between the patient and the needle in order for the participant not to see that no water will be injected. The blind used will be a drape or other soft item held by a person not involved with the study to obscure the vision of the subject during the sham injection and allow the investigator to use both hands to safely conduct the sham injection procedure. After the needle is removed the area will be cleaned with alcohol swabs and a bandage will be applied. Four separate needles and syringes will be utilized for each location. This will be completed on POD 0 (ie the day of the TKA procedure). Within the informed consent the consenting verbiage will ensure that the participants will not be able to identify injection technique that will identify whether they are in the sham or experimental group.

Step 4: On POD0 (after TKA surgery, the investigator will review MHS Genesis to obtain demographic information (age, sex, beneficiary status, BMI), morphine milligrams equivalents (MME) using the Medication Administration Record (MAR) Summary, prior pain medication history, diabetic history, tobacco use, anesthetic block type, surgical site, ICD codes, complications, and discharge disposition.

Step 5: On POD1, participants in each study group will be provided with the VAS and Opioid Use questionnaires. The VAS pain scale questionnaire will be used to report average pain scores by placing a hash mark (/) on the numbered scale

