on the region that best represents their pain and writing the number (a whole number) on the form; scores range from 0 (no pain) to 100 (severe intolerable pain). The Opioid Use questionnaire will be used to document average opioid use following discharge. Both questionnaires will be completed by all participants at POD1, week 2 and week 6 visits. The VAS will be given to the participant with the intake form that is provided by the orthopedic technician, and the investigator will provide the Opioid Use questionnaire to the participant during the visit, and review the MAR Summary to obtain and calculate the total MME from POD0 to POD1 using MDCalc . Prior to ending the visit, the investigator will ask participants to bring in their opioids to be physically counted at their week 2 and week 6 visits.

Step 6: The investigator will provide a reminder phone call 1-2 days prior to the week 2 and week 6 appointments to ensure participants remember to bring in their medication.

Step 7: Participants return for the week 2 and week 6 visits. They are given VAS and Opioid Use questionnaires to complete, and opioid medication is counted. Once opioids have been accounted for, MME will be calculated.

10.2 Data Collection:

Describe all the data variables, information to be collected, the source of the data, and how the data will be operationally measured.

Injection type: Dichotomous variable. Trigger point or sham injection.

Visual analogue scale: Discrete variable. Will be scaled from 0 (no pain) to 100 (severe intolerable pain) and will be measured at POD1, week 2, and week 6. The VAS will be presented to the participant on paper.

Morphine milligram equivalent (MME): Discrete variable. Will be measured from POD 0 to POD1, then a total MME will be calculated from POD1 to week 2 and week 2 to week 6. This will be calculated utilizing the MME calculator on MDCalc.

Block: Categorical variable. Spinal, adductor or femoral nerve block determined by anesthesiology.

Age: Continuous variable. Age stated in years at time of surgery as stated in EHR.

Prior Pain Medications: Categorical variable. Obtained from EHR.

Discharge disposition: Dichotomous variable. Discharge to skilled nursing facility or home, discharge disposition will be reviewed in the discharge summary.

Active Duty, Dependent, Retiree: Categorical Variable.

Sex: Categorical (male, female). Obtained from EHR.

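### Section 11.1 lets discharge disposition, which is settled after the injection, trigger and enter covariate adjustment; it is a possible result of treatment, and adjusting for it can bias the VAS comparison

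*Combined protocol and SAP*

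**What the plan says.** Section 11.1 lists the variables to be described and compared between groups: age, BMI, sex, beneficiary status, ICD code, nicotine use, diabetes, prior pain medication, and then "laterality of the TKA (left or right), discharge disposition, and anesthetic block type (spinal, adductor, or femoral nerve block"). Any that differ significantly set off the rule: "If so, multivariable techniques (eg, ANOVA or regression) including these potentially confounding variables in the analyses and/or stratification will be undertaken". One alpha of .05 is given for all tests. Nothing exempts disposition or separates variables fixed before the injection from those fixed after it.

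On timing, Section 10.1 Step 3a says of the injection: "This will be completed on POD 0 (ie, the day of the TKA procedure"). Section 10.2 defines disposition thus: "Discharge to skilled nursing facility or home, discharge disposition will be reviewed in the discharge summary". Step 4 of Section 10.1 also lists disposition, in a POD 0 record review. The two places do not agree on when it is captured, but the Step 4 review takes place after surgery and is listed after the Step 3 injection.

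On the outcome, Section 10.1 says of the VAS and opioid forms: "Both questionnaires will be completed by all participants at POD1, week 2 and week 6 visits". Section 11.5 names the independent samples t test, or the Wilcoxon Mann Whitney test, for the primary VAS comparison. Section 11.1 does not say whether an adjusted analysis, once triggered, replaces that test or sits beside it.

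**The concern.** A confounder must precede treatment. Ten of the eleven variables do. Block type is one of them, since Step 3b relies on the block when the injection is given: "Since the effects from the anesthetic block will still be active". Disposition is the exception.

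The plan's own expectations make an effect of the injection on disposition plausible. Section 9.6 hopes for "shorter inpatient stays and decrease adverse medication side effects", and Section 14.4 for better recovery and easier physical therapy. That such gains would also change where patients go on discharge is an inference; the documents do not say so.

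If they do, a working injection makes the groups differ on disposition, the difference triggers adjustment, and the adjusted model compares patients with the same disposition. That comparison no longer estimates the whole effect of the injection. Allocation is by alternation (Section 10.1 Step 2), so an adjusted result may be read as the safer one, although under this rule it need not be.

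**Working it through.** **Inputs from the documents.** True difference 28 and SD 25 (11.5); 15 or 10 per group (11.5); ceiling of 50 per group (11.2); two-sided alpha .05 (11.1, 11.5).

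**The plan's own figure.** d = 28/25 = 1.12, stated as 1.1. Wilcoxon power can be approximated by a noncentral t with n' = n × 3/π per group and noncentrality d√(n'/2).
- 15 per group: n' = 14.32, 1.1 × √7.16 = 2.94, power 0.81.
- 10 per group: n' = 9.55, 1.4 × √4.77 = 3.06, power 0.82.

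Both stated sizes reproduce. They do not depend on the adjustment rule.

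**Mechanism.** In a linear model of VAS on group and disposition,

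adjusted difference = unadjusted difference − b × (p_sham − p_trt),

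where b is the within-group VAS difference between facility and home patients and p is the proportion sent to a facility. If b is zero nothing changes. If b is positive and the injection lowers p, the adjusted figure is smaller.

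Example at 50 per group, assuming a 40% sham facility rate and an odds ratio of 4 per SD of pain: simulated p is 0.400 against 0.170, the unadjusted difference is 28.0 and the adjusted 22.0. The implied b is 6.0/0.230 = 26.1. The rule fires in 74% of such trials (0.738), where the unadjusted mean is 29.0. In the rest it is (28.0 − 0.738 × 29.0)/0.262 = 25.2. The plan-wide mean is 0.738 × 22.0 + 0.262 × 25.2 = 22.8.

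**Range, with disposition depending only on VAS.** Assumed, because the documents give nothing: normal VAS, sham mean 60, SD 25; logit P(facility) = (VAS − c)/s; the same VAS is analysed; adjustment only if disposition differs at p < .05. Section 11.1 has a Fisher fallback, "Exact test if assumption regarding minimum expected cell counts is not met", but states it for the VAS > 40 comparison. It does not say whether the fallback also covers the screening tests, so both versions are shown at 15 per group. Cells give the share of trials flagged and the plan-wide mean for a true 28.

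| c, s | Sham facility rate | 15/group, chi-square | 15/group, Fisher fallback | 50/group, chi-square |
|---|---|---|---|---|
| 60, 12 | 50% | 43%, 21.8 | 36%, 22.6 | 90%, 18.8 |
| 60, 20 | 50% | 29%, 24.8 | 25%, 25.2 | 73%, 22.9 |
| 75, 20 | 36% | 26%, 25.5 | 16%, 26.3 | 67%, 23.8 |
| 75, 30 | 39% | 19%, 26.6 | 13%, 27.0 | 46%, 25.9 |
| 100, 20 | 17% | 12%, 27.0 | 5%, 27.6 | 44%, 26.0 |
| 110, 20 | 12% | 6%, 27.5 | 2%, 27.8 | 32%, 26.8 |

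The fallback alters only the last two rows at 50 per group (26.1 and 27.0). At 10 per group the means are 23.5 to 27.8 with chi-square and 25.4 to 27.9 with the fallback. Other checks:
- A later VAS correlating 0.4 (assumed) with early pain: 25.5 to 27.9 at 15 per group, 24.2 to 27.6 at 50.
- A true difference of 15 at 15 per group: bias 0.1 to 2.2 units, against a standard error of 25√(2/15) = 9.1.
- Disposition unrelated to pain: mean 28.0, no bias.

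**No true VAS effect.** If disposition depends only on VAS, the mean stays at zero. Now let the injection also act directly on disposition, lowering the log-odds of a facility by an assumed 1 to 2 logits, in the (60, 20) and (75, 20) cases. The unadjusted difference is zero and p_sham exceeds p_trt, so the formula gives a negative benefit, that is, apparent harm. The simulated bias is about 1 to 5 units at 15 per group and 2.5 to 7.8 at 50. At 50 per group, rejection rises to between about .08 and .35, against .05 unadjusted. A direct effect of the opposite sign would reverse the direction.

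**The case against.** The strongest reply is that little is exposed at the planned size. Section 11.5 names an unadjusted test for the primary comparison, so on that wording only a conditional further analysis is affected. The lower end of the range, 21.8, needs half of sham patients to go to a facility and an odds ratio of exp(25/12), about 8, per SD of pain. With sham rates of 10-40% and odds ratios of 2 to 4 per SD, the rule fires in about 1-21% of trials at 15 per group and the plan-wide mean is 25.6 to 28.1. Section 11.5 also says that the cited dry-needling trial saw less than 28 units at one month, and the bias shrinks with the effect. Fifty per group is a ceiling that depends on time and resources.

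All of this stands as to size, and it is why the point is minor at 10-15 per group. It does not answer the text. Disposition is in the list, the rule has no exemption, and 11.1 does not say what a triggered adjusted analysis does to the primary test.

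Three stronger readings are tempting and are not supported:
- A reader might infer that the primary VAS result is biased. Section 11.5 points the other way; the documents leave the matter open.
- A reader might infer that the rule can only dilute a real effect and so cannot produce a false positive. That holds only if the injection reaches disposition solely through VAS and nothing unmeasured drives both. The documents do not establish either condition.
- A reader might infer that the whole screening rule biases the estimate. Chance may help to choose covariates at this size, but no bias is shown for the ten pre-injection variables.

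**Conclusion.** The point holds in limited form. Discharge disposition is determined after the injection, yet Section 11.1 allows it to trigger and enter adjustment or stratification as though it were a baseline variable. If disposition responds to pain and the injection works, part of the VAS effect is removed. With a direct effect on disposition, or a shared unmeasured cause, the bias can take either sign and can arise with no true VAS effect. The shared-cause case was not simulated.

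The size cannot be fixed from the documents. With disposition driven only by VAS and a true difference of 28, the assumed scenarios give a plan-wide mean of about 22 to 28 at 15 per group and about 19 to 27 at 50. At sham facility rates of 12-17% the bias is about 1 unit or less at 15 per group and about 1 to 2 units at 50. Severity is therefore minor at 10-15 per group, and greater if enrolment approaches 50 per group, because the rule then fires more often. The defect in the text is certain; its numerical effect rests on the assumed rates and slopes.

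**What to change.** In Section 11.1:
1. Remove discharge disposition from the variables that can trigger or enter adjustment or stratification, and restrict that rule to variables fixed before the injection, for VAS and MME alike.
2. Report disposition by group as a post-treatment outcome.
3. State that the unadjusted t or Wilcoxon Mann Whitney test in 11.5 is the primary VAS analysis and that any adjusted analysis is supporting.

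Section 10.1 Step 4 and Section 10.2 should also agree on when disposition is captured.

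The cost is wording only. No new data are needed, and the primary test and sample size are unchanged.

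Optionally, a short covariate list chosen before outcomes are seen could replace significance screening. This is a trade-off and is not needed to cure the defect. A list using 4 degrees of freedom (for example age, any prior pain medication, and block type) gives the supporting model power of about 0.78 against 0.84 unadjusted (15 per group, 28 units), or 0.73 against 0.84 (10 per group, 35 units), if the covariates predict nothing. It breaks even when they explain about 15-20% of VAS variance at 15 per group, or 20-30% at 10. None of this addresses possible selection through predictable alternation, which is a separate matter.

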There have been limited studies aimed at the treatment of myofascial pain syndrome in the acute setting of a TKA. Mayoral et al. (2013) conducted a randomized double-blinded, placebo-controlled clinical trial where patients who underwent a TKA had dry needling completed in the pre-operative and intra-operative setting. This study demonstrated an improvement in pain scores within the first month of surgery in the dry needling group compared to a sham group. This has been the only study to date to address direct intervention for myofascial pain syndrome around the operative time frame. Henry et al. (2012) conducted a prospective study in which patients on the waitlist for a TKA were treated with trigger point injections; patients reported an improvement in pain up until the TKA procedure could be completed. Although Henry et al. did not assess pain in the post-operative setting, this study nonetheless demonstrated that myofascial pain syndrome is a component of osteoarthritis.

Despite these favorable results there are no studies that look at trigger point injections in the post-surgical setting. The aim of this study is to perform trigger point injections with administration of a local anesthetic immediately following TKA to assess the effect on pain scores. The trigger point injection/experimental group will be compared to a sham injections/control group where a superficial injection will be made into the dermis and no anesthetic will be injected. Injections will include two injections to four muscle bellies: the vastus medialis, vastus lateralis, medial, and lateral gastrocnemius muscle belly. Injections will include 0.5 mL of lidocaine without epinephrine and will be outside of the operative area distal and proximal to the joint, the popliteal fossa and incision site. With each injection the plunger will be pulled back to ensure placement of the needle is outside vascular structures. To assess the primary outcome measures, patients will complete a Visual Analogue Scale (VAS) which ranges from 0 (no pain) to 100 (severe intolerable pain) on post operative day (POD) 1 and at follow-up visits during weeks 2 and 6. The secondary outcome will assess how much opioid medication (ie, MME) was used in the immediate post-operative period through the week 6 follow-up visit.

9.3

Objectives/Specific Aims/Research Questions:

Describe the purpose and objective(s) of the study, specific aims, and/or research questions /hypotheses

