11.5 Please provide a justification for your sample size

We used G*Power 3.1 (Dusseldorf Germany) to perform sample size calculations for our study. We designed these calculations using the primary outcome measure (ie, VAS pain scale rating in each injection group) which will be statistically compared using the independent samples t test or its nonparametric equivalent (ie, the Wilcoxon Mann Whitney test) if the assumptions for the independent samples t test (ie, normality and homogeneity of variance) are not met.

Using the more conservative Wilcoxon Mann Whitney test (Type 1 error/alpha level=.05 (two tailed) and power=.80), a sample size of 30 (ie, 15 in the trigger point group and 15 in the sham group) would allow us to detect a statistically significant difference in VAS pain scale ratings if a “large” effect size of 1.1 was obtained. A “large” effect size of 1.1 corresponds to an average difference (delta) in VAS scores between groups of ≥ 28 units and an average standard deviation in each group of ≤ 25 units. This standard deviation is similar to Mayoral et al. (2013) who reported an average standard deviation of 25 units for the VAS at the 1 month follow up. Note that Mayoral et al. (2013) did not report VAS scores on POD1, although their average difference (delta) in VAS scores at 1 month was smaller than 28 units.

If up to 5 patients (eg, 30%) per group drop out of the study, a lower sample size of 20 (ie, 10 in the trigger point group and 10 in the sham group) would allow us to detect a statistically significant difference in VAS pain scale ratings if a larger effect size of 1.4 was obtained. This “larger” 1.4 effect size corresponds to an average difference (delta) in VAS scores between groups of ≥ 35 units and an average standard deviation in each group was ≤ 25 units (again using the more conservative Wilcoxon Mann Whitney test (Type 1 error/alpha level=.05 (two tailed) and power=.80)).

In summary, our aim of including at least 10-15 patients per group would allow us to statistically detect a “large” effect of trigger point injections (relative to sham injections) on VAS pain ratings assuming our standard deviations were \leq to the standard deviations in VAS pain scales reported by Mayoral et al. (2013). In addition, if statistically significant differences are not found, the data from our

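### VAS is primary at three visits, each compared at .05, with no primary visit, test order or adjustment; the sample size claim is tied to no named visit

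*Combined protocol and SAP*

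**What the plan says.** - Section 9.2 ties the primary outcome, in the plural, to the VAS: "To assess the primary outcome measures, patients will complete a Visual Analogue Scale (VAS" is how the sentence begins, and it goes on to list POD1, week 2 and week 6. Opioid use (MME) is secondary.
- Section 9.3 repeats the three visits without ranking them: "Outcomes include the VAS on POD1 and week 2 and week 6 follow-up appointments".
- Section 11.1 states that VAS and MME "will be evaluated in patients as a function of injection type (ie, trigger point injection vs. sham injection) at each time point". It leaves the method to the data, choosing whether "parametric (eg, independent samples t tests, repeated measures ANOVAs) or nonparametric (eg, Wilcoxon Mann Whitney tests, Skillings-Mack tests) methods are appropriate". VAS above 40 is also "compared in each group and at each time point using the chi-square test" or Fisher's exact test. On error control it says only "The critical alpha level will be set at .05".
- Section 11.5 sizes the study on the primary outcome measure, now in the singular, "which will be statistically compared using the independent samples t test or its nonparametric equivalent" (Wilcoxon Mann Whitney). It uses two-sided alpha .05, power .80, effect size 1.1 and 15 per group, or effect size 1.4 and 10 per group after dropout. No visit is attached to that comparison. The SD of 25 comes from the 1-month follow-up of an earlier dry-needling trial, which 11.5 notes did not report POD1 scores.

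**The concern.** Three comparisons share primary status, each at an unadjusted .05, while the sample size rests on one. Two things follow. First, the 80% power in 11.5 belongs to no identified comparison, so a reader cannot tell which result the study was sized to deliver. Second, if the three visits disagree, nothing in the plan says which one answers the primary question. A visit chosen after the groups have been compared cannot be shown to have been chosen independently of the results, and the nominal 5% would then no longer describe the chance of a false primary claim.

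**Working it through.** **Inputs from the documents.** Three VAS visits (9.2, 9.3); alpha .05 (11.1), two-sided with power .80 (11.5); effect size d = 1.1 with 15 per group and d = 1.4 with 10 per group (11.5). **Assumed, because the documents do not give it:** the correlation between visits, varied from 0 to 0.9, equal for all pairs, with normal data.

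**1. Reproduce the plan's sample size.** For the Wilcoxon test, use the noncentral t with n multiplied by the asymptotic relative efficiency 3/π = 0.955. The noncentrality is d × √(0.955n/2), on 2(0.955n) − 2 degrees of freedom.
- n = 15, d = 1.1: noncentrality 1.1 × √(14.32/2) = 2.94, critical value 2.05, power 0.81.
- n = 10, d = 1.4: noncentrality 1.4 × √(9.55/2) = 3.06, critical value 2.11, power 0.82.

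Both stated sample sizes are the smallest that reach 80%. The arithmetic in 11.5 is correct for one test at one visit.

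**2. False-positive rate if any of the three visits counted.** With uncorrelated visits it is 1 − (1 − .05)³ = 1 − 0.857 = 0.143. For the exact Wilcoxon at 15 per group the attainable level is 0.0453, so the figure is 1 − 0.9547³ = 0.130. With correlated visits, simulation at 15 per group (200,000 runs) gives:

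| Correlation (assumed) | t test | Exact Wilcoxon |
|---|---|---|
| 0 | 14.2% | 12.9% |
| 0.5 | 12.7% | 11.8% |
| 0.7 | 11.0% | 10.2% |
| 0.9 | 8.5% | 8.1% |

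The range is therefore about 8% to 14%. Its lower end needs a correlation near 0.9. These figures cover the three VAS comparisons only, not VAS above 40 or MME.

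**3. Power if all three visits stay primary with an adjustment**, at 15 per group and d = 1.1.
- Bonferroni, alpha .05/3 = .0167. Wilcoxon: noncentrality 2.94, critical value 2.55, power per visit 0.65 (down from 0.81). t test: noncentrality 3.01, critical value 2.55, power 0.68 (down from 0.83).
- Holm with t tests, if d = 1.1 holds at all three visits: average per-visit power 0.76 at correlation 0.5 and 0.74 at 0.9 (simulation).
- For 80% per visit with Wilcoxon under Bonferroni, 19 per group gives 0.78 and 20 per group gives 0.81.

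**The case against.** The strongest reply is that this is a small study whose stated aim in 9.3 is to explore, and that 11.5 already foresees a null result being used to size later work. That stands as far as it goes: descriptive reporting of all three visits would be defensible, and it is why the point is not rated higher. It does not remove the point, because 11.5 attaches a .05 level and 80% power to a primary outcome, and those claims need an identified comparison.

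Two stronger readings are tempting, and the documents support neither. A reader might infer that this trial's false-positive rate is 8% to 14%. The plan states no rule that any visit suffices, so that figure is conditional on such a rule and on an assumed correlation. A reader might also infer that the primary test itself is unspecified. Section 11.5 does state the test family; what is missing is the visit, and any order or adjustment across visits.

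It can also be said that repeated measures ANOVA in 11.1 supplies one overall group test, which would hold 5%. It is listed only as an example beside t tests, no effect in it is named as primary, and 11.5 is not sized on it. Finally, the remark in 11.5 that the earlier trial had no POD1 scores may hint that POD1 was in mind. It is a caveat about source data and does not choose a visit; the SD it accompanies comes from 1 month, which is not a visit in this trial.

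**Conclusion.** The point holds as a gap in commitment and should be fixed. Three visits are primary, each is compared at .05, and neither a primary visit nor any control across visits is stated. The sample size is arithmetically right for one comparison at a visit it does not identify. If significance at any visit were taken as the primary result, the false-positive rate over the three VAS tests would be about 8% to 14%. That rests on an any-visit rule the plan does not state but does not exclude, on a between-visit correlation of 0.9 down to 0 that is assumed, and on normal data at 15 per group. The absence of a named visit can be read directly from 9.2, 9.3, 11.1 and 11.5 and needs none of these assumptions.

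**What to change.** Before any outcome data are compared, name one visit as the single primary VAS endpoint, in the same words in 9.2, 9.3, 11.1 and 11.5, tested once at two-sided .05 with the test 11.5 states. Report the other VAS visits and VAS above 40 as secondary, with estimates and 95% confidence intervals; MME is already secondary. The visit is the investigators' choice. Section 11.5 should then tie its SD and delta assumptions to that visit and say plainly where they are carried over from the earlier trial's 1-month data.

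This costs wording in four sections and no added patients. The downside is that a result seen only at a non-primary visit cannot be claimed as the primary result.

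If all three visits matter equally, keep them all primary, state the adjustment and restate the power in 11.5. At 15 per group and d = 1.1 that is about 65% per visit with Wilcoxon under Bonferroni (68% with the t test), or about 74% to 76% on average with t tests under Holm if the effect holds at all visits. Reaching 80% per visit with Wilcoxon under Bonferroni takes about 20 per group, within the maximum of 50 per group in 11.2.
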